3.3.4.1 Discontinuation of trial treatment

An individual subject will discontinue trial treatment if:

1. The subject wants to discontinue trial treatment, without the need to justify the decision
2. The subject has repeatedly shown to be non-compliant with important trial procedures and, in the opinion of both, the investigator and sponsor representative, is not willing or able to adhere to the trial requirements in the future.
3. The subject needs to take concomitant medication that interferes with the investigational medicinal product or other trial treatment
4. The subject can no longer receive trial treatment for medical reasons (such as surgery, adverse events [AEs], or diseases)
5. The subject has an elevation of AST and/or ALT ≥ 3 -fold upper limit of normal (ULN) and an elevation of total bilirubin ≥ 2 -fold ULN (measured in the same blood sample) and/or needs to be followed up according to the DILI checklist provided in the ISF.
6. The subject experiences a drug-related serious adverse event or drug-related severe adverse event. AEs will be considered as drug-related unless clearly unrelated (e.g. events prior to administration of study drug), see Section [5.1.5.1.6](#).

In addition to these criteria, the investigator may discontinue subjects at any time based on his or her clinical judgment.

Even if the trial treatment is discontinued, the subject remains in the trial and, given his/her agreement, will undergo the procedures for early treatment discontinuation and follow up as outlined in the [Flow Chart](#) and Section [6.2.3](#).

3.3.4.2 Withdrawal of consent to trial participation

Subjects may withdraw their consent to trial participation at any time without the need to justify the decision. If a subject wants to withdraw consent, the investigator should be involved in the discussion with the subject and explain the difference between trial treatment discontinuation and withdrawal of consent to trial participation, as well as explain the options for continued follow up after trial treatment discontinuation, please see Section [3.3.4.1](#) above

3.3.4.3 Discontinuation of the trial by the sponsor

Boehringer Ingelheim reserves the right to discontinue the trial at any time for any of the following reasons:

1. Failure to meet expected enrolment goals overall or at a particular trial site
2. New toxicological findings, serious adverse events, or any safety information invalidating the earlier positive benefit-risk-assessment. More specifically, the trial will be terminated or suspended if more than 50% of the subjects have drug-related and clinically relevant adverse events of moderate or severe intensity, if more than two subjects have drug-related non-serious adverse events of severe intensity or if at least 1 drug-related serious adverse event is reported. AEs will be considered as drug-related unless clearly unrelated (e.g., events prior to administration of study drug), see Section [5.1.5.1.6](#).

Any further dosing is only possible after an analysis and evaluation of the harm, review of

Proprietary confidential information © 2018 Boehringer Ingelheim International GmbH or one or more of its affiliated companies

the risk-benefit analysis, submission of a substantial amendment for further dosage and approval by the competent authority and ethics committee.

3. Violation of GCP or the CTP impairing the appropriate conduct of the trial-
4. The sponsor decides to discontinue the further development of the investigational product

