4.1.3 Method of assigning subjects to treatment groups

The randomisation list will be provided to the trial site in advance.

Subjects will be allocated to treatment sequences prior to the first administration of trial medication in the morning of Day 1 (Visit 2). For this purpose, numbers of the randomisation list will be allocated to the subjects by drawing lots. Subjects are then assigned to a treatment sequence according to the randomisation list.

Once a subject number has been assigned, it cannot be reassigned to any other subject.

All subjects may be treated in one cohort, i.e. all subjects may receive treatment on the same calendar day. In case this is not feasible (e.g., due to logistical or recruitment reasons), the group may be split into several cohorts as required. Treatment of all subjects on the same calendar day is acceptable (for safety margin to exposure reached in SRD trial 1405-0001 and for discussion of study-associated risks and safety measures, see Section 1.4).

The randomisation procedure is described in Section [7.6](#).

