5.1.5.1.6 Causal relationship of AEs

Medical judgment should be used to determine the relationship, considering all relevant factors, including pattern of reaction, temporal relationship, de-challenge or re-challenge, confounding factors such as concomitant medication, concomitant diseases and relevant history.

Arguments that may suggest that there is a reasonable possibility of a causal relationship could be:

- The event is consistent with the known pharmacology of the drug
- The event is known to be caused by or attributed to the drug class
- A plausible time to onset of the event relative to the time of drug exposure

- Evidence that the event is reproducible when the drug is re-introduced
- No medically sound alternative aetiologies that could explain the event (e.g. pre-existing or concomitant diseases, or co-medications)
- The event is typically drug-related and infrequent in the general population not exposed to drugs (e.g. Stevens-Johnson syndrome)
- An indication of dose-response (i.e. greater effect size if the dose is increased, smaller effect size if dose is reduced)

Arguments that may suggest that there is no reasonable possibility of a causal relationship could be:

- No plausible time to onset of the event relative to the time of drug exposure is evident (e.g. pre-treatment cases, diagnosis of cancer or chronic disease within days / weeks of drug administration; an allergic reaction weeks after discontinuation of the drug concerned)
- Continuation of the event despite the withdrawal of the medication, taking into account the pharmacological properties of the compound (e.g. after 5 half-lives). Of note, this criterion may not be applicable to events whose time course is prolonged despite removing the original trigger
- Additional arguments amongst those stated before, like alternative explanation (e.g. situations where other drugs or underlying diseases appear to provide a more likely explanation for the observed event than the drug concerned)
- Disappearance of the event even though the trial drug treatment continues or remains unchanged

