5.1.5.2 Adverse event collection and reporting

5.1.5.2.1 AE collection

Upon enrolment into a trial, the subject's baseline condition is assessed (for instance, by documentation of medical history/concomitant diagnoses), and relevant changes from baseline are noted subsequently.

Subjects will be required to report spontaneously any AEs as well as the time of onset, end time, and intensity of these events. In addition, each subject will be regularly assessed by the medical staff throughout the clinical trial and whenever the investigator deems necessary. As a minimum, subjects will be questioned for AEs (and concomitant therapies) at the time points indicated in the [Flow Chart](#). Assessment will be made using non-specific questions such as 'How do you feel?'. Specific questions will be asked wherever necessary in order to more precisely describe an AE.

A carefully written record of all AEs shall be kept by the investigator in charge of the trial. Records of AEs shall include data on the time of onset, end time, intensity of the event, and any treatment or action required for the event and its outcome.

The following must be collected and documented on the appropriate CRF(s) by the investigator:

- From signing the informed consent onwards until an individual subject's end of trial:

Proprietary confidential information © 2018 Boehringer Ingelheim International GmbH or one or more of its affiliated companies

- All AEs (serious and non-serious) and all AESIs
- The only exception to this rule are AEs (serious and non-serious) and AESIs in Phase I trials in healthy volunteers, when subjects discontinue from the trial due to screening failures prior to administration of any trial medication. In these cases, the subjects' data must be collected at trial site but will not be entered in the CRF or trial database and will not be reported in the CTR.
- After the individual subject's end of trial:
 - The investigator does not need to actively monitor the subject for AEs but should only report any occurrence of cancer and related SAEs and related AESIs of which the investigator may become aware of by any means of communication, e.g. phone call. Those AEs should, however, not be reported in the CRF.

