5.1.5.2.2 AE reporting to the sponsor and timelines

The Investigator must report SAEs, AESIs, and non-serious AEs which are relevant for the reported SAE or AESI, on the BI SAE form via fax immediately (within 24 hours) to the sponsor's unique entry point (country specific contact details will be provided in the ISF). The same timeline applies if follow-up information becomes available. In specific occasions the Investigator could inform the sponsor upfront via telephone. This does not replace the requirement to complete and fax the BI SAE form.

With receipt of any further information to these events, a follow-up SAE form has to be provided. For follow-up information, the same rules and timeline apply as for initial information.

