7.6 RANDOMISATION

Subjects will be randomised to one of the 2 treatment sequences in a 1:1 ratio. The block size will be documented in the CTR.

The sponsor will arrange for the randomisation as well as packaging and labelling of trial medication. The randomisation list will be generated using a validated system that uses a pseudo-random number generator and a supplied seed number so that the resulting allocation is both reproducible and non-predictable.

The randomisation list will contain additional blocks to allow for subject replacement (refer to Section [3.3.5](#)).

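### Could a late serious adverse event that meets the stop rule go unreported because 'related' is not tied to one meaning throughout the protocol?

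*Protocol*

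**What the plan says.** The trial-level stop rule in Protocol 3.3.4.3 has several triggers. The one at issue applies "if at least 1 drug-related serious adverse event is reported". The same paragraph sets the causality standard, "AEs will be considered as drug-related unless clearly unrelated", and refers to Section 5.1.5.1.6. Section 3.3.4.1, on stopping treatment in an individual, uses the same presumption and the same cross-reference.

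Section 5.1.5.1.6 itself reads differently: "Medical judgment should be used to determine the relationship, considering all relevant factors". It then lists arguments for and against a reasonable possibility of a causal link and states no default.

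Reporting depends on timing. Up to a subject's end of trial, Section 5.1.5.2.1 has all adverse events collected. Section 5.1.5.2.2 sets a 24-hour limit with no causality condition: "The Investigator must report SAEs, AESIs, and non-serious AEs which are relevant for the reported SAE or AESI". After a subject's end of trial, Section 5.1.5.2.1 says the investigator "should only report any occurrence of cancer and related SAEs and related AESIs of which the investigator may become aware", and adds: "Those AEs should, however, not be reported in the CRF".

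Dosing need not end for everyone at once. Section 4.1.3 allows all subjects to be dosed on one calendar day, but if that is not feasible "the group may be split into several cohorts as required". Section 7.6 provides for later entrants: "The randomisation list will contain additional blocks to allow for subject replacement".

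**The concern.** The stop rule and the reporting rule appear to use different tests of relatedness. An SAE for which another cause is more likely, though not certain, could be judged unrelated on the arguments in 5.1.5.1.6 and still fall short of being clearly unrelated. During a subject's participation this does no harm, because the sponsor receives every SAE and can apply the presumption itself. After that subject's end of trial the investigator's own reading of 'related' acts as the filter.

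A single reported event is enough to halt the trial, so one event held back at that filter could matter if other subjects still had doses to come. Such events also stay out of the CRF, so the SAE tables in SAP 7.8.1 would not show them. A second, smaller worry is that the report might describe a suspension for a drug-related SAE while the drug-related SAE table shows none.

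**Working it through.** The plan gives no figure to reproduce here; the point turns on wording. Setting the sections side by side:

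1. **Is there a contradiction?** Section 3.3.4.3 states a presumption, 5.1.5.1.6 describes how to weigh causality, and 5.1.5.2.1 uses 'related' without definition. Section 5.1.5.1.6 sets no numerical or verbal threshold; it lists considerations that may point either way. The presumption is phrased for adverse events in general and directs the reader to the causality section, so it can be taken as the meaning for the whole trial. The texts are ambiguous and do not plainly conflict. That post-trial reporting drops the presumption is an inference from silence.

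2. **Does anything else catch a late event?** Protocol 7.3.4, repeated in SAP 7.8.1, says that events after the last per-protocol contact but entered before database lock go to Pharmacovigilance. It sets no relatedness condition. What counts as entered is not spelled out, so this route is not watertight, but it prevents the conclusion that the event must be lost.

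3. **Is the one-SAE trigger the only way to stop?** No. The same item of 3.3.4.3 opens with a general ground: new toxicology findings, serious adverse events or any other safety information that overturns the benefit-risk assessment. No causality test is attached to it.

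4. **What must coincide for harm?** All four of these:
   - a non-cancer SAE starts after that subject's own end of trial;
   - the investigator learns of it, since active monitoring has ended;
   - it is judged neither related nor clearly unrelated;
   - other subjects still have doses to come.

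   The last condition needs split cohorts, replacements, or an early end-of-trial visit after discontinuation (Section 6.2.3). If all 12 subjects are dosed in one cohort and complete both periods without replacement, essentially no dosing remains.

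5. **Could the tables mislead about events during participation?** SAP 7.8.1 lists relationship among the recorded attributes of each event, and Protocol 7.3.4 says causal relationship is tabulated. SAP 7.8.1 also plans a table of subjects with SAEs regardless of cause. An SAE during participation that led to a suspension would therefore appear there, even if recorded as unrelated.

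6. **How common might this be?** Section 1.2.4.1 reports no severe or serious events in the single rising dose trial, in which 48 subjects received BI 1323495. For 0 events in 48, the exact 95% upper limit per subject is
   - one-sided: 1 − 0.05^(1/48) = 0.0605, about 6.1%;
   - two-sided: 1 − 0.025^(1/48) = 0.0740, about 7.4%.

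   These limits concern any severe or serious event seen within that trial. They are not rates of disputed events after a subject's end of trial, for which the documents give nothing.

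**The case for a change.** The best case for acting is that the two descriptions of causality can give different answers. Section 5.1.5.1.6 treats a more likely alternative explanation as an argument against a causal link, and a more likely alternative does not make an event clearly unrelated. The presumption appears only in 3.3.4.1 and 3.3.4.3. Amendment 1 lists both among the changed sections and lists neither 5.1.5.1.6 nor 5.1.5.2.1, so the alignment may simply have been left unfinished. The protocol does not commit to one cohort. The residual effect period is unknown (Section 1.2.5), so the questioning of early leavers at or after its end (Section 3.3.4) has no defined window. The same word also bears on individual discontinuation, replacement and the drug-related tables, and clarifying it would take only a few sentences.

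Much of this stands as an observation about drafting. The cross-reference does lead to a section that lacks the presumption, and 'related' is undefined in 5.1.5.2.1. What does not stand is the step from there to a lost stop signal. That step requires the narrow reading of 5.1.5.2.1, no use of the Pharmacovigilance route in 7.3.4, and all four conditions above. For replacement, no actual conflict with Section 3.3.5 has been shown. For the tables, a cautious stop rule can sit beside tables of causality as recorded, because the two serve different purposes.

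**Conclusion.** No change to the plan follows. This is missing detail of a kind that the investigator and sponsor can settle in the ordinary handling of safety reports. Following the plan as written has not been shown to give a wrong result. SAEs during a subject's participation are unaffected, the relative bioavailability estimates and their 90% confidence intervals are untouched, and the remaining exposure is one narrow combination of circumstances whose frequency the documents do not give.

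The conclusion rests on three assumptions: that SAEs during participation are reported whatever their cause, as 5.1.5.2.2 requires; that 7.3.4 means what it says about later events; and that the tables use the relationship recorded for each event. The length of any exposed window cannot be assessed, because the Flow Chart that sets the end-of-trial timing is not shown. Sections 3.3.4.1, 3.3.4.3, 5.1.5.1.6, 5.1.5.2.1 and 7.3.4 have to be read together. Reconciling their wording is a low-priority clarification should the protocol be reopened for another reason. Which meaning of 'related' governs is for the sponsor to say.

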3.3.5 Replacement of subjects

Subjects withdrawn due to drug related adverse events will not be replaced. In case some subjects do not complete the trial for any other reason, the Trial Clinical Monitor together with the Trial Pharmacokineticist and the Trial Statistician are to decide, if and how many subjects will be replaced. A replacement subject will be assigned a unique trial subject number, and will be assigned to the same treatment as the subject replaces.

4. TREATMENTS

4.1 INVESTIGATIONAL TREATMENTS

The investigational product has been manufactured by BI Pharma GmbH & Co. KG.

4.1.1 Identity of the Investigational Medicinal Products

The characteristics of the test product are given below:

Substance: BI 1323495

Pharmaceutical formulation: Tablet, film-coated

Source: BI Pharma GmbH & Co. KG, Germany

Unit strength:

Posology: 2-0-0

Route of administration: oral

Duration of use: single dose in treatment T and R

4.1.2 Selection of doses in the trial and dose modifications

In the ongoing first in man trial (1405-0001) it is planned to investigate single doses up to BI 1323495. In this food effect trial, it is intended to administer two single doses of BI 1323495. This dose has been chosen as it corresponds to the assumed therapeutic dose (see Section [1.2.2](#)).

The investigator in this trial 1405-0007 will be informed by the sponsor in writing about the outcome of the documented safety review meeting scheduled after completion of the dose group in trial 1405-0001.

Proprietary confidential information © 2018 Boehringer Ingelheim International GmbH or one or more of its affiliated companies

Based on the experience gained during trial 1405-0001, a lower dose of BI 1323495 may be tested in this trial. If the lower dose is selected for safety reasons, this will be implemented via substantial amendment only.

4.1.3 Method of assigning subjects to treatment groups

The randomisation list will be provided to the trial site in advance.

Subjects will be allocated to treatment sequences prior to the first administration of trial medication in the morning of Day 1 (Visit 2). For this purpose, numbers of the randomisation list will be allocated to the subjects by drawing lots. Subjects are then assigned to a treatment sequence according to the randomisation list.

Once a subject number has been assigned, it cannot be reassigned to any other subject.

All subjects may be treated in one cohort, i.e. all subjects may receive treatment on the same calendar day. In case this is not feasible (e.g., due to logistical or recruitment reasons), the group may be split into several cohorts as required. Treatment of all subjects on the same calendar day is acceptable (for safety margin to exposure reached in SRD trial 1405-0001 and for discussion of study-associated risks and safety measures, see Section 1.4).

The randomisation procedure is described in Section [7.6](#).

4.1.4 Drug assignment and administration of doses for each subject

This trial is a 2-way crossover study. All subjects will receive the 2 treatments in randomised order. The treatments to be evaluated are outlined in Table [4.1.4: 1](#) below.

Table 4.1.4: 1 Dosage and treatment schedule

Treatment	Substance	Formulation	Unit strength	Dosage	Total dose
T (Test)	BI 1323495	Tablet, film-coated		as single dose, fed state	
R (Reference)	BI 1323495	Tablet, film-coated		as single dose, fasted state	

Administration of trial medication will be performed after subjects have fasted overnight; fasting is to start no later than 10 h before the scheduled dosing.

In treatment T, a high-fat, high-calorie meal will be served within 30 min before drug administration. The subjects must completely consume the meal prior to drug intake. The composition of the standard high-fat, high-calorie meal is detailed in Table [4.1.4: 2](#); this meal is in compliance with the FDA guidance ‘Food-Effect Bioavailability and Fed Bioequivalence Studies’ ([R03-2269](#)). For restrictions with regard to diet, see Section [4.2.2.2](#).

Table 4.1.4: 2 Composition of the high-fat, high-calorie meal

Ingredients	kcal
2 chicken eggs (whole content) for scrambled eggs	192
10 g butter for frying scrambled eggs	75

Proprietary confidential information © 2018 Boehringer Ingelheim International GmbH or one or more of its affiliated companies

Ingredients	kcal
35 g fried bacon	186
2 toasted slices of wheat bread	130
15 g butter for buttering toast slices	113
115 g hash brown potatoes	132
240 mL whole milk (3.5% fat)	156
Sum¹	984

¹ The total caloric content was supplied approximately as following: 150 kcal as protein, 250 kcal as carbohydrate, and 500 to 600 kcal as fat.

The investigator (or authorised designee) will administer the trial medication as an oral dose together with about 240 mL of water to subjects who are in a standing position. For drug administration, the so-called four-eye principle (two-person rule) should be applied. For this, one authorised employee of the trial site should witness the administration of trial medication, and – if applicable – its preparation (e.g. reconstitution), if correct dosage cannot be ensured otherwise.

Subjects will be kept under close medical surveillance until 24 h after drug administration. During the first 4 h after drug administration, subjects are not allowed to lie down (i.e. no declination of the upper body of more than 45 degrees from upright posture).

The treatments will be separated by a wash-out phase of at least 6 days.

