5.1.2 Vital signs

Systolic and diastolic blood pressures (BP) as well as pulse rate (PR) or heart rate (heart rate is considered to be equal to pulse rate) will be measured by a blood pressure monitor (Dinamap Pro 100, GE Medical Systems, Freiburg, Germany) at the times indicated in the [Flow Chart](#), after subjects have rested for at least 5 min in a supine position. All recordings should be made using the same type of blood pressure recording instrument on the same arm, if possible.

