5.1.4 Electrocardiogram

Twelve-lead ECGs (I, II, III, aVR, aVL, aVF, V1 - V6) will be recorded using a computerised electrocardiograph (CardioSoft EKG System, GE Medical Systems, Freiburg, Germany) at the times provided in the [Flow Chart](#).

To achieve a stable heart rate at rest and to assure high quality recordings, the site personnel will be instructed to assure a relaxed and quiet environment, so that all subjects are at complete rest.

All ECGs will be recorded for 10 sec duration after subjects have rested for at least 5 min in a supine position. ECG assessment will always precede all other study procedures scheduled for the same time to avoid compromising ECG quality.

All ECGs will be stored electronically on the Muse CV Cardiology System (GE Medical Systems, Freiburg, Germany). Electrode placement will be performed according to the method of Wilson, Goldberger and Einthoven modified by Mason and Likar (hips and shoulders instead of ankles and wrists).

All locally printed ECGs will be evaluated by the investigator or a designee. Abnormal findings will be reported as AEs (during the trial) or baseline conditions (at screening) if assessed to be clinically relevant by the investigator. Any ECG abnormalities will be carefully monitored and, if necessary, the subject will be removed from the trial and will receive the appropriate medical treatment.

ECGs may be repeated for quality reasons (for instance, due to alternating current artefacts, muscle movements, or electrode dislocation) and the repeated ECG will be used for analysis. Additional (unscheduled) ECGs may be collected by the investigator for safety reasons.

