6. INVESTIGATIONAL PLAN

6.1 VISIT SCHEDULE

Exact times of measurements outside the permitted time windows will be documented. The acceptable time windows for screening, for measurements and assessments scheduled to occur ‘before’ trial medication administration on Day 1, and the end of trial examination are provided in the [Flow Chart](#).

The acceptable deviation from the scheduled time for vital signs, ECG and laboratory tests will be ± 15 min for the first 4 h after trial drug administration and ± 30 min thereafter. Starting from 48 h post administration a deviation from the scheduled time for vital signs, ECG and laboratory tests of ± 120 min is acceptable.

If scheduled in the [Flow Chart](#) at the same time as a meal, blood sampling, vital signs, and 12-lead ECG recordings have to be done first. Furthermore, if several measurements including venepuncture are scheduled for the same time, venepuncture should be the last of the measurements due to its inconvenience to the subject and possible influence on physiological parameters.

For planned blood sampling times, refer to the [Flow Chart](#). While these nominal times should be adhered to as closely as possible, the actual sampling times will be recorded and used for the determination of pharmacokinetic parameters.

If a subject misses an appointment, it will be rescheduled if possible. The relevance of measurements outside the permitted time windows will be assessed no later than at the Report Planning Meeting.

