11. DESCRIPTION OF GLOBAL AMENDMENT(S)

11.1 GLOBAL AMENDMENT 1

Date of amendment	22 November 2018	
EudraCT number	2018-002792-18	
EU number		
BI Trial number	1405-0007	
BI Investigational Medicinal Product(s)	BI 1323495	
Title of protocol	Relative bioavailability of BI 1323495 following oral administration under fed and fasted conditions in healthy male subjects (an open-label, randomised, single-dose, two-period, two-sequence crossover study)	
To be implemented only after approval of the IRB / IEC / Competent Authorities		
To be implemented immediately in order to eliminate hazard – IRB / IEC / Competent Authority to be notified of change with request for approval		
Can be implemented without IRB / IEC / Competent Authority approval as changes involve logistical or administrative aspects only		
Section to be changed	1	Flow Chart
	2	Section 1.2.4 Clinical experience in humans
	3	Section 1.4 Benefit – Risk Assessment
	4	Section 3.3.3 Exclusion criteria
	5	Section 3.3.4.1 Discontinuation of trial treatment
	6	Section 3.3.4.3 Discontinuation of the trial by the sponsor
	7	Section 3.3.5 Replacement of subjects
	8	Section 4.1.3 Method of assigning subjects to treatment groups
	9	Section 5.1.3 Safety laboratory parameters
	10	Section 5.2.2.1 Blood sampling for pharmacokinetic analysis

Proprietary confidential information © 2018 Boehringer Ingelheim International GmbH or one or more of its affiliated companies

Description of change	1	PK sampling schedule adapted based on SRD data; additional ECG/VS at 2h postdose
	2	Preliminary data from SRD trial 1405-0001 amended
	3	Benefit – risk assessment amended based on data gained in SRD trial.
	4	Exclusion criterion 20 more precisely described
	5	Additional criterion for individual treatment discontinuation introduced.
	6	Discontinuation of the trial by the sponsor, point 2 clarified by more detailed description.
	7	Clarification: subjects withdrawn for drug related AEs will not be replaced.
	8	Explanation that all subjects may be dosed in one cohort on the same calendar day.
	9	Test name of drug screen corrected.
	10	PK blood samples may be stored at room temperature until centrifuged.
Rationale for change	1	In the SRD trial, maximum plasma concentrations were reached earlier than expected based on preclinical data; therefore the sampling schedule for PK was adapted accordingly

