6.7 BASELINE, TIME WINDOWS AND CALCULATED VISITS

For vital signs baseline for Period 1 is defined as the last measurement prior to first drug administration, and baseline for Period 2 is defined as the last measurement prior to first drug administration in Period 2.

For laboratory parameters baseline for Period 1 and Period 2 is defined as the last measurement prior to first drug administration, as the REP of BI 1323495 is not known.

Section 6.1 of the CTP: *Exact times of measurements outside the permitted time windows will be documented. The acceptable time windows for screening, for measurements and assessments scheduled to occur 'before' trial medication administration on Day 1, and the end of trial examination are provided in the Flow Chart.*

The acceptable deviation from the scheduled time for vital signs, ECG and laboratory tests will be ± 15 min for the first 4 h after trial drug administration and ± 30 min thereafter. Starting from 48 h post administration a deviation from the scheduled time for vital signs, ECG and laboratory tests of ± 120 min is acceptable.

If scheduled in the Flow Chart at the same time as a meal, blood sampling, vital signs, and 12-lead ECG recordings have to be done first. Furthermore, if several measurements including venepuncture are scheduled for the same time, venepuncture should be the last of the measurements due to its inconvenience to the subject and possible influence on physiological parameters.

Adherence to time windows will be checked via the consistency check listings at the RPM/DBLM.

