7.8.3 Vital signs

Descriptive statistics including change from baseline will be performed for vital signs (blood pressure and pulse rate) by treatment.

Clinically relevant findings in vital signs will be reported as AEs.

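### Does the 4 h ban on lying down after dosing make the supine ECG and vital signs at 2 h impossible to perform as written?

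*Protocol*

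**What the plan says.** Four parts of the protocol and two of the SAP bear on the point.

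- **Posture after dosing (Protocol 4.1.4).** "During the first 4 h after drug administration, subjects are not allowed to lie down". Lying down is defined by an angle: "no declination of the upper body of more than 45 degrees from upright posture". No exception for study procedures is stated there.
- **Measurement posture (Protocol 5.1.2 and 5.1.4).** Vital signs are taken at the Flow Chart times "after subjects have rested for at least 5 min in a supine position". For ECGs: "All ECGs will be recorded for 10 sec duration after subjects have rested for at least 5 min in a supine position".
- **Schedule (Protocol 11.1, first change listed).** The amendment altered the Flow Chart to include an "additional ECG/VS at 2h postdose".
- **Time window (Protocol 6.1, repeated in SAP 6.7).** Vital signs, ECGs and laboratory tests may deviate by ±15 "min for the first 4 h after trial drug administration".
- **Baseline (SAP 6.7).** "For vital signs baseline for Period 1 is defined as the last measurement prior to first drug administration". Period 2 has its own pre-dose baseline.
- **Analysis (SAP 7.8.3 and 7.8.4).** "Descriptive statistics including change from baseline will be performed for vital signs (blood pressure and pulse rate) by treatment". ECGs are read by the investigator for abnormal findings, and no change from baseline is planned for them.

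**The concern.** Read literally, the sections collide at 2 h. A supine subject lies well beyond the 45 degree limit, and the 2 h assessment sits in the middle of the restricted period. The protocol gives an order of precedence for other clashes (ECG before other procedures, measurements before meals, venepuncture last) but none for posture.

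Two things would be at stake. First, staff could break one rule at each 2 h assessment, and SAP 6.2 has deviations from the protocol identified for all treated subjects. Second, if staff kept subjects upright or semi-recumbent at 2 h after a supine baseline, the change from baseline in blood pressure and pulse rate at that time point would contain a posture effect as well as any drug or food effect.

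**Working it through.** The plan gives no figure to reproduce. The check is one of timing, followed by what each reading of the text does to the planned summaries.

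**Timing** (inputs: 2 h assessment from Protocol 11.1, ±15 min from 6.1, 5 min rest from 5.1.2 and 5.1.4, 4 h restriction from 4.1.4)

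- Earliest reading: 120 − 15 = 105 min after dosing.
- Latest reading: 120 + 15 = 135 min.
- Latest start of a 5 min rest: 135 − 5 = 130 min.
- End of restriction: 4 × 60 = 240 min.
- Gap from the latest reading: 240 − 135 = 105 min. Gap from the latest start of rest: 240 − 130 = 110 min.

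No permitted timing moves the assessment out of the restricted period.

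**Posture.** Supine is about 90 degrees from upright and the limit is 45 degrees, so the two descriptions do not overlap.

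**Number of occasions.** 12 subjects × 2 periods = 24 at most. This assumes that all subjects complete and that the 2 h assessment is scheduled in both periods. That gives up to 24 vital-sign sets that enter change-from-baseline summaries and up to 24 ECGs that do not.

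**Effect on the summaries under each reading**

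1. *The Flow Chart exempts these measurements.* There is no conflict and no effect.
2. *No exemption, and staff follow 5.1.2 and 5.1.4.* Baseline and 2 h readings are both supine. The change from baseline is measured as intended, and the only consequence is a brief departure from 4.1.4.
3. *No exemption, and staff follow 4.1.4.* The 2 h reading is not supine but the baseline is. Let p be the posture shift in a vital sign, and d_T and d_R the true changes under fed and fasted dosing. The recorded changes are d_T + p and d_R + p. Each is shifted by p, but their difference is (d_T + p) − (d_R + p) = d_T − d_R. The fed-fasted comparison is intact if posture is handled alike in both periods and p does not depend on food.

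The documents give no value for p, so the shift in reading 3 cannot be sized. It would affect the 2 h vital signs. Whether other measurements fall in the first 4 h cannot be counted from the visible text.

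**Primary analysis.** AUC and Cmax come from plasma concentrations and are compared within subject on the log scale (Protocol 7.3.1). Nothing in the documents ties the posture of the 2 h vital signs to that model.

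**The case for a change.** The strongest opposing argument is that the contradiction is real on the visible page and costs one clause to remove. The restriction is precise, down to an angle, and carries no exception. The ECG rule covers all ECGs. Amendment 1 lists 4.1.3 among its changed sections but not 4.1.4, 5.1.2 or 5.1.4, so none of the conflicting sections was listed for revision when the 2 h assessment was added. Nor does the point depend on a superseded entry in the change log: that entry describes what the current Flow Chart contains, and the ±15 min window independently implies some measurement in the first 4 h.

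Most of this stands. The quotations are accurate, the arithmetic is right, and no exemption appears in the visible text of either document.

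The step from there to an unavoidable deviation does not stand. Sections 5.1.2, 5.1.4 and 6.1 leave the timing of these measurements to the Flow Chart, and the Flow Chart is the first item on the amendment's list of changed sections. A footnote there would be an ordinary place for an exemption. Its absence from the extracted text is not evidence that the plan lacks one.

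The posture-mixing argument also needs reading 3. The text equally allows 4.1.4 to be read as governing how subjects spend the 4 h, with short procedures following their own sections, although it does not say so expressly. Variation between sites is not a worry either, because SAP 6.5 describes a single centre.

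**Conclusion.** The tension in the wording is genuine but conditional, and it does not call for a change to the design or the analysis. It is a drafting query. If the Flow Chart already exempts supine ECGs and vital signs, a cross-reference in 4.1.4 is all that is missing. If it does not, Sections 4.1.4, 5.1.2 and 5.1.4 must be reconciled for the first 4 h, with the same handling in the fed and fasted periods. Which rule prevails is for the sponsor, and this review takes no position on it.

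The reach is small: at most 24 dosing occasions and, under one of three readings, a shift in the 2 h change from baseline for blood pressure and pulse rate. Those summaries are descriptive and no hypothesis testing is planned for safety (Protocol 7.3.4). The ECG evaluation has no change-from-baseline component, and no effect on AUC, Cmax or the pharmacokinetic model is shown.

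This rests on three assumptions: the 2 h assessment applies in both periods, all 12 subjects complete, and the single site handles posture alike in both periods. The Flow Chart could settle the first.
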